Rationale for clinician nudge using mortality prediction and peer comparison. Due to optimism bias, clinicians routinely overestimate the life expectancy of patients with advanced cancer^{28,29} and delay SICs until too late in the disease course. In part because of this, clinicians reinforce a social norm that early SICs are not part of routine oncology care. Providing an objective assessment of predicted mortality risk may help counteract optimism bias among clinicians, and help them identify patients most likely to benefit from SICs. Moreover, that individuals desire to conform to an approved behavior (an injunctive norm) and the behavior of others (a descriptive norm) may contribute to low observed SIC rates, and may also afford an opportunity for intervention. We expect that periodically reminding clinicians of their own performance on SIC documentation, while providing both an injunctive norm (citing national and institutional guidelines) and a descriptive social norm (displaying the behavior of their best performing peers), will lead clinicians to conform more closely to these norms, as has been shown in studies conducted in other contexts.^{23,30,31}

Rationale for patient nudge using priming. Priming is a type of nudge that frames information to activate one's self-efficacy and willingness to engage in behavior change.³² This type of nudge has not previously been evaluated as a tool to promote SICs for patients with cancer. We will test the added impact of a patient nudge designed to prime patients and, in turn, their clinicians to having a SIC.

CHARACTERISTICS OF THE STUDY POPULATION:

1. Target Population and Accrual:

The target population includes approximately 5,500 high-risk patients with cancer cared for by approximately 166 medical and gynecologic oncology clinicians at the following hospital and free-standing community practice sites of the Penn Medicine Abramson Cancer Center (ACC), referred to hereafter as the "Implementation Laboratory": Hospital of the University of Pennsylvania (HUP), Pennsylvania Hospital (PAH), Penn Presbyterian Medical Center (PPMC), Chester County Hospital (CCH), Valley Forge Medical Center, Radnor Medical Center, Cherry Hill Medical Center, Voorhees Medical Center, Sewell Medical Center and Regional Hematology Oncology Associates. The trial will be conducted pragmatically, and patients will accrue as they are seen in follow-up at a participating practice site by an eligible provider.

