Eligible clinicians and patients will be identified using the criteria listed above, and will be independently randomized to study arms using a 2x2 factorial design. Eligible clinicians will be randomized *at the start of the study* and will receive nudges identifying their high-risk patients with or without peer comparisons for the duration of the study period. Eligible patients will be randomized *in advance of an index outpatient clinical encounter*, and will accrue to the study accordingly. Patients will be exposed to implementation strategies based on their assigned study arm, which will depend on their own randomization and that of their clinician (determined at the time of the index outpatient clinical encounter). Physicians will be mapped to advanced practitioners (i.e. physician assistants, nurse practitioners) with whom they work, and vice versa, and this cluster will serve as the clinician unit of analysis and thus will be cluster randomized.

Nudge to clinician only. The clinician nudge will consist of targeted text messages identifying patients at high risk of predicted 6-month mortality based on a validated machine learning prognostic algorithm,^{33,34} as well as SIC documentation performance feedback graphically compared to peers (“clinician peer comparison”). The clinician nudge will be delivered weekly via email with text messages sent on the morning(s) before clinic sessions. See **Appendix 1. Sample Provider Nudge** for the content of provider nudge email and text.

Nudge to patient only. The patient nudge will consist of a normalizing message prompting patients to complete an electronic questionnaire designed to prime patients towards having a SIC (“patient priming”). The nudge will be delivered via text message and email in advance of the index clinical encounter, and will be re-sent a maximum of two times at monthly intervals only for those patients who neither fill out the priming questionnaire nor have a documented SIC during follow-up. Patient-reported data from the priming questionnaire will be shared with clinical teams in real-time. See **Appendix 2. Sample Patient Nudge** for the content of patient nudge texts, email, and electronic questionnaire.

Nudges to both clinician and patient. Both strategies described above will be used.

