- *Ecologic-level data* linked at the patient- and practice-level, including median income and educational attainment.

Aim 3

Aim 3 data collection will additionally consist of patient-reported content obtained during the course of the study in response to the SIC priming questionnaire, among 1,166 participants randomized to the patient nudge study arm who completed the SIC priming questionnaire (Appendix 2).

3. Genetic Testing:

Not applicable

4. Use of Deception:

Not applicable

5. Statistical Analysis:

Aim 1

The primary outcome will be modeled in a time-to-event analysis using a Cox proportional hazards model, with cluster-correlated robust standard errors to account for clustering by clinical site. SIC documentation, as defined above, will serve as the primary event outcome. Days between the index clinical encounter (at which the nudge exposure period begins) and SIC documentation will serve as the time variable. The design is a 2x2 factorial, which breaks down into 4 study arms (defined by clinician cluster and patient randomization at the index clinical encounter): nudge to clinician only, nudge to patient only, nudge to both, or usual practice. Cox regression will estimate hazard ratios for the main effects (Aim 1) and a ratio of hazard ratios for the interaction term (Aim 2). Significance will be determined using the z-score corresponding to each of the estimated effects, using a two sided type 1 error of 5%. All enrolled patients will be included in the intention-to-treat analysis, and subjects will be censored at the time of last follow-up or death, should they

not have been observed to have a documented SIC during the follow-up period. Covariates will be assessed across study arms and included in the Cox model if unbalanced across arms.

We will use our fitted Cox model to generate predicted probabilities of SIC documentation within 6 months, via marginal standardization, as well as median time to documented SIC across arms. The functional form of the model will be checked using cumulative martingale residuals, and the proportional hazards assumption will be checked using scaled Schoenfeld residuals.

The secondary outcomes will be similarly modeled. All hypothesis tests will use a two-sided alpha of 0.05 as the threshold for statistical significance.

Aim 2

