We are seeking to detect the main effects of nudges and their interaction with at least 80% power using a two-sided alpha of 0.05. We anticipate enrolling 66 physician-APP clusters who will together care for an estimated 5,500 high-risk patients over the study period, yielding approximately 83 high-risk patients per cluster on average. We have generated power calculations using various patient enrollment and cluster correlation assumptions as below. We calculated power by simulation, generating exponential time to event under a variety of assumptions. Patients are clustered within clinician units. Higher correlation within cluster will generally help with power for within-cluster comparisons, but degrade power for between-cluster comparisons. Within cluster correlation was imposed by drawing correlated Normally-distributed random numbers, transformed to exponential using copula methods.

Patients per Cluster	Within Cluster Correlation	Detectable True HR of Effect (Power)		
		Provider nudge	Patient nudge	Interaction

70	0.1	1.6 (86%)	1.25 (84%)	1.6 (80%)
70	0.3	2.0 (85%)	1.3 (90%)	1.8 (91%)
90	0.1	1.6 (91%)	1.25 (86%)	1.6 (85%)
90	0.3	2.0 (86%)	1.25 (84%)	1.6 (83%)

Assuming conservatively that we enroll 70 patients per cluster with a cluster correlation of 0.1, we will have >80% power to detect a true hazard ratio of effect of HR 1.6 for the provider nudge, HR 1.25 for the patient nudge, and HRR 1.6 for the interaction. Assuming 70 patients per cluster and a cluster correlation of 0.3, we will have >80% power to detect a true hazard ratio of effect of HR 2.0 for the provider nudge, HR 1.3 for the patient nudge, and HRR 1.8 for the interaction. These estimates improve slightly if we assume enrollment of 90 patients per cluster, allowing us to detect similar effect sizes with more power, as shown in the Table above.

RISK/BENEFIT ASSESSMENT:

1. Risks:

There are minimal risks to participants in this trial. There is a risk of breach of data and confidentiality, however we described the precautions in place to securely manage this data in the Data Management section of this protocol. As noted above, substantial data demonstrates that ACPs improve patient goal-concordant care without any identified harms (despite concerns that ACPs may increase psychosocial distress, the opposite has been found), so the negative impact on patients is minimal.

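### The primary Cox model takes its robust standard errors by clinical site, but the trial randomises and is powered on 66 physician-APP clusters

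*Combined protocol and SAP*

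**What the plan says.** Under Statistical Analysis, Aim 1, the primary outcome is analysed by a Cox model "with cluster-correlated robust standard errors to account for clustering by clinical site". The same paragraph describes the arms as "defined by clinician cluster and patient randomization at the index clinical encounter" and continues: "Significance will be determined using the z-score corresponding to each of the estimated effects", at a two-sided 5% level. It then adds "The secondary outcomes will be similarly modeled".

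Study Procedures, Detailed Description, links physicians to the advanced practitioners they work with and says "this cluster will serve as the clinician unit of analysis and thus will be cluster randomized". Power and Sample Size says "We anticipate enrolling 66 physician-APP clusters" with about 83 high-risk patients each, and of the simulation model it says "Patients are clustered within clinician units".

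Target Population and Accrual names ten hospitals and community practices. The documents do not say that these are the clinical sites of the variance calculation, how many units each contains, or whether a unit works at only one of them. No few-cluster correction is mentioned.

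**The concern.** The primary test carries two clustering levels. An analyst following the Aim 1 paragraph would cluster by site. One following the Detailed Description or the power section would cluster by physician-APP unit. The standard errors and p-values differ.

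Read literally, the site rule has a specific weakness. A sandwich variance compared with a normal z needs many clusters, and about ten is too few: the variance is estimated imprecisely and, without a correction, is too small on average. All three tests in the factorial model would reject too often and their confidence intervals would be too narrow. The secondary outcomes inherit the rule.

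If the wording is a slip, the sentence still leaves the clustering level to be settled at analysis.

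**Working it through.** **Inputs from the documents.** 66 physician-APP clusters and 5,500 high-risk patients, so 5,500/66 = 83.3 per cluster, which agrees with the stated 83. Within-cluster correlation 0.1 or 0.3; exponential times with a Gaussian copula; 6 months of follow-up; z-test at two-sided 5%.

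**Assumptions.** Ten sites (a count of the names listed), each unit in one site, and a 15% six-month event rate. None of these is stated in the documents.

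**The plan's own figure.** The power table cannot be reproduced from the documents alone, because no baseline event rate or censoring is given. With an assumed 10% baseline rate and unit clustering, the provider-nudge cell (70 per cluster, correlation 0.1, HR 1.6) gives 86.0% against the stated 86%. No single rate among 8%, 10% and 12% matches all 12 cells. The type I error result does not depend on this table.

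**Analytic check.** With G equal-sized clusters the robust z behaves approximately as t on G−1 degrees of freedom. With the G/(G−1) factor, the error is P(|t(G−1)| > 1.96). Without it, the error is P(|t(G−1)| > 1.96·√((G−1)/G)). For G = 10 the second cut-off is 1.96 × √0.9 = 1.859.

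| Clusters G | With factor | Without factor |
|---|---|---|
| 8 | 9.1% | 10.9% |
| 10 | 8.2% | 9.6% |
| 12 | 7.6% | 8.7% |
| 66 | 5.4% | 5.6% |

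**Simulation under the null.** 66 units × 83 patients, correlation 0.1, 33 versus 33 units, patients 1:1; 23,767 datasets, Monte Carlo SE 0.1–0.3 points. Near-equal sites hold 6 or 7 units each. Main effects come from the two-term model and the interaction from the three-term model.

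| Variance and reference | Clinician | Patient | Interaction |
|---|---|---|---|
| Ten sites, z, with factor | 8.3% | 8.3% | 8.6% |
| Ten sites, z, without factor | 9.8% | 9.7% | 10.0% |
| 66 units, z | 5.8% | 5.7% | 6.0% |
| 66 units, factor and t(64) | 5.2% | 5.0% | 5.4% |

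With 8 to 12 similar-sized sites the site-clustered range is 7.7–9.5% with the factor and 9.0–11.4% without. One assumed uneven layout (24, 10, 7, 6, 5, 4, 4, 2, 2, 2 units) gives 11.3–11.6% and 12.9–13.2%.

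**Other assumptions.** A separate simulation varied the baseline rate (10–50%), the correlation (0.1 or 0.3) and extra site correlation (0, 0.05 or 0.15), with ten near-equal sites and Monte Carlo SE about 0.5–0.9 points. The clinician test rejected in 8.4–9.6% with the factor and 9.9–11.4% without; the patient test in 7.1–8.6% and 7.8–10.3%. Unit clustering gave 5.4–6.8% for the clinician test. Ten sites with the factor and t(9) gave 4.8–6.3%.

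**Standard errors, clinician-nudge log HR.** Empirical SD 0.153; mean robust SE 0.149 by unit, 0.140 by near-equal site and 0.130 by uneven site.

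**Aim 2 limit on the remedy.** A null nudge-by-moderator term was simulated with a site-level moderator (4 of 10 sites flagged) and both nudge effects varying by site. Monte Carlo SE was 0.4–1.0 points. Unit clustering with the correction gave:

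| SD of site-varying log HR (assumed) | Clinician nudge | Patient nudge |
|---|---|---|
| 0 | 6.3% | 5.1% |
| 0.15 | 6.3% | 11.4% |
| 0.3 | 10.6% | 19.6% |

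The literal site-clustered z gave 12.3–14.4% in the same runs. A two-stage t-test on site-specific log hazard ratios held 4.3–5.8%. For patient-level and clinician-level moderators, unit clustering with the correction gave 3.9–6.8%.

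**The case against.** The strongest reply is that the word site is a slip. Three other statements in the plan point to the physician-APP cluster, including the Aim 1 paragraph's own definition of the arms. On that reading the error is about 6%. This may well be the intent. It does not remove the conflict, because the sentence that specifies the variance says something else, and Target Population uses the word sites for hospitals and practices, not clinician teams.

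Second, the site count, sizes and nesting are assumed, and more clusters would shrink the inflation: P(|t(G−1)| > 1.96) is 7.0% at G = 15 and 6.5% at G = 20. This stands. The 8–10% is conditional, and the uneven layout shows it can also be larger.

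Third, site is not an invalid level in itself. If units are nested in sites, site clustering captures the within-unit correlation, and with the factor and t(9) it performs about as well as unit clustering with z. This also stands. The fault on the literal reading is few clusters with a normal reference, so a corrected site-level analysis is a legitimate alternative.

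Fourth, the Aim 2 text names no clustering level, and its simulations rest on assumed site variation. That is fair. They are used here only to limit how far the Aim 1 remedy should be extended.

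**Conclusion.** The concern holds. The plan gives two incompatible clustering levels for its primary test, and that finding rests on the text alone. The size is conditional: with ten similar-sized sites, each unit in one site, and an uncorrected z-test, type I error is about 8% (factor applied) to 10% (not applied) for the clinician, patient and interaction tests. Clustering on the 66 units gives about 6%, or about 5% with a small-sample correction. On the wording-slip reading there is little inflation, but the sentence is still wrong. Because it governs the primary analysis and carries over to the secondary outcomes, it must be corrected before analysis.

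**What to change.** In Statistical Analysis, Aim 1, state that robust standard errors are clustered on the randomised physician-APP unit, for the primary outcome, the secondary outcomes and the clinician-by-patient nudge interaction. G/(G−1) with a t reference on about 64 degrees of freedom is an optional refinement.

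In Aim 2, use unit clustering for patient-level and clinician-level moderators only. For moderators constant within a site, such as practice setting, urban location and practice-linked census measures, use a few-cluster method at site level, for example comparing site-specific log hazard ratios with a t reference. Otherwise label those tests exploratory.

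If clustering by site is really intended, define site, give the number of sites and of units in each, and add a few-cluster correction. In either case state which variance estimator the power simulation used.

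**Cost.** One sentence for Aim 1 and one for Aim 2, with no new data. With near-equal sites, the rounded mean SEs give intervals 0.149/0.140 − 1 = 6.4% wider than a literal plan without the factor, and 0.149/(0.140 × √(10/9)) − 1 = 1.0% wider than one with it. Unrounded values and a repeat run put these at about 7–8% and 2%. In the uneven layout the figures are about 14–15% and 9%. The optional correction adds about 3%. Site-level moderator tests on about ten sites will have low power.

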Usual practice. Usual practice will consist of targeted text messages identifying patients at high risk of mortality based on a validated machine learning prognostic algorithm, as well as clinician-directed performance feedback (WITHOUT peer comparison), thereby serving as an active control arm.

We will use RCA to optimize implementation strategies to ensure face validity and maximum effect. We will focus on optimizing content, messaging, and design. RCA procedures will involve design meetings with study team, discussions with administrators and clinicians who are members of our Implementation Lab, as well as piloting of nudges with clinicians and patients to elicit feedback.

2. Data Collection:

The electronic medical record and other Penn Medicine secondary databases will be used to collect information on practices, clinicians, and patients. These systems collect this information as part of routine clinical care. We will also collect data from the U.S. Census via publicly available datasets.

Aim 1

The primary outcome is SIC documentation among high-risk patients. This will be measured at the patient level as a binary outcome, ascertained over the 6-month period following the index outpatient clinical encounter. The electronic medical record has an Advanced Care Planning (ACP) section in which ACP notes are documented. Any note documented in this section will be classified as an ACP, and only the subset of notes that include a preformatted SIC template will be classified as a SIC.

The secondary outcomes will each be measured at the patient level as a binary outcome, ascertained over the 6-month period following the index outpatient clinical encounter:

- SIC documentation, among all patients
- Palliative care referral, among high-risk patients
- Aggressive end-of-life care (any of the following three criteria: chemotherapy within 14 days before death, hospitalization within 30 days before death, or admission to hospice 3 days or less before death), among high-risk patients who die

Aim 2

Aim 2 measures, collected through the electronic medical record and using publically available U.S. Census data, will include:

- *Patient-level data*: age, sex, race/ethnicity, cancer type, cancer stage, health insurance (e.g., Medicare, Medicaid, commercial);
- *Clinician-level data*: years in practice and patient panel size;
- *Practice-level data*: setting (community vs. hospital-based), urban vs. non-urban location, and health insurance mix;

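### The primary Cox model's only covariate rule selects on observed imbalance, with metric, threshold and level left open; fix a minimal set led by the clinician unit's baseline SIC rate instead

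*Combined protocol and SAP*

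**What the plan says.** The rule is a single sentence under STUDY PROCEDURES, 5. Statistical Analysis, Aim 1: "Covariates will be assessed across study arms and included in the Cox model if unbalanced across arms". It names no covariates, no measure of imbalance and no cut-off. It does not say whether balance is judged over clinician units or over patients. The same section says "The design is a 2x2 factorial, which breaks down into 4 study arms", so the comparison could be across four groups or across the two levels of each factor. Secondary outcomes are to be modelled in the same way and so inherit the rule.

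Three other parts of the plan bear on it:

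- **Unit of randomisation.** Physicians and their advanced practitioners are grouped, and "this cluster will serve as the clinician unit of analysis and thus will be cluster randomized" (Detailed Description). The Aim 1 model is to be fitted "with cluster-correlated robust standard errors to account for clustering by clinical site".
- **Candidate variables.** Data Collection lists 13 measures, introduced by "Aim 2 measures, collected through the electronic medical record and using publically available U.S. Census data, will include". The clinician-level items are "years in practice and patient panel size" and the practice-level items are "setting (community vs. hospital-based), urban vs. non-urban location, and health insurance mix". None is a SIC documentation rate before randomisation. The Aim 2 analysis uses such factors as interaction terms, not as an adjustment set.
- **Design-stage control of balance.** No stratified randomisation is described.

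**The concern.** Adjustment in a randomised trial earns its place through prognostic value. A rule that looks only at imbalance can admit irrelevant covariates and leave out strong predictors that happen to balance. With 66 randomised units, sizeable differences in unit characteristics are expected by chance. With thousands of patients, the same differences look highly significant if patients are treated as independent. The unstated details therefore settle which model is primary.

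Two things are at stake. First, the plan does not determine the primary analysis, so the model could be settled after results are known. Second, the clinician-nudge contrast is made between units, where the power section itself says correlation costs power. That is where a prognostic unit-level covariate could help, and the rule does not ensure that one is kept.

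**Working it through.** **Inputs.** From Power and Sample Size: 66 physician-APP units, 70 patients per unit (conservative case), correlation 0.1 with HR 1.6 or 0.3 with HR 2.0, exponential times with a copula, 5% two-sided level. From Data Collection: 6 months of follow-up. Assumed: 33 units per clinician arm, patients 1:1 within unit, control 6-month SIC probability 12%, baseline SIC rate explaining 30% of between-unit variance (R2), standard errors clustered by clinician unit. Paired results below are correlation 0.1 / 0.3.

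**1. The plan's own power.** The control rate is not stated. At 12%, simulation gives 85.8% for the clinician nudge, against the stated 86% (70 patients, correlation 0.1). At correlation 0.3 a 15% rate is needed (85.2% against 85%). No single rate tried reproduced all four rows of the table, so 12% is an assumption.

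**2. How often a unit-level covariate counts as unbalanced.** With 33 against 33 units, the chance SMD has standard deviation 2/√66 = 0.246.

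- Unit-level 5% test: 5% by construction.
- SMD > 0.25: 0.25/0.246 = 1.02, so P(|Z| > 1.02) ≈ 31%.
- SMD > 0.10: 0.10/0.246 = 0.41, so ≈ 68%.
- Patient-level 5% test, 66 × 70 = 4,620 patients: cut-off 1.96 × 2/√4,620 = 0.058; 0.058/0.246 = 0.23, so ≈ 81%.

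The readings are nested, so they disagree in about 81 − 5 = 76% of trials. This step needs no event rate or R2. Over four arms, simulation gives 39% (largest pairwise SMD > 0.25), 79% (> 0.10) and 78% (patient-level ANOVA).

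**3. Type I error, clinician nudge, z-test.** Simulation with 20,000 runs gives:

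- unadjusted: 6.1-6.2 / 6.3-6.5%;
- any one trigger fixed in advance: 5.0-5.9 / 5.2-6.3%;
- best of the four readings in step 2: 7.8 / 8.2%;
- free choice of adjusted or unadjusted: 8.8-9.1 / 9.2-9.7%.

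A second set of 3,000 runs gives 9.0 / 9.9% for free choice, against 5.8 / 6.4% unadjusted.

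A separate simulation (10% control rate, 1,200 runs) allows a check by P(either significant) = (U + A + D)/2, where U and A are the unadjusted and adjusted rejection rates and D is the rate of disagreement. At correlation 0.1:

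- R2 25%: (6.4 + 7.1 + 4.2)/2 = 8.9%;
- R2 50%: (6.4 + 7.2 + 6.4)/2 = 10.0%;
- R2 80%: (6.4 + 6.4 + 8.5)/2 = 10.7%.

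**4. Power at equal Type I error, clinician nudge.** Each strategy is held to its own simulated 5% critical value (20,000 runs; Monte Carlo error about 0.5 point).

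| Handling of one unit covariate | corr. 0.1, HR 1.6 | corr. 0.3, HR 2.0 |
|---|---|---|
| Never adjusted | 84.1% | 77.2% |
| Unit-level 5% trigger | 85.9% | 79.4% |
| SMD > 0.25 trigger | 89.1% | 83.5% |
| SMD > 0.10 trigger | 90.3% | 85.1% |
| Patient-level 5% trigger | 90.4% | 85.4% |
| Always adjusted | 90.7% | 85.7% |

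Always adjusting gains 90.7 − 84.1 = 6.6 and 85.7 − 77.2 = 8.5 points over none, 4.8 and 6.3 over the unit-level trigger, and 0.3-1.6 / 0.3-2.2 over the looser triggers. Over the four-arm readings the gain is 0.3-1.2 / 0.3-1.3. With practice setting added to both sides, the gains are 4.6-6.7 over a unit-level trigger and 0.2-2.3 over looser ones. The second set of runs gives 84.0 to 90.6% and 76.3 to 85.7% against no adjustment. Allowing for that set and for Monte Carlo error, I round to 7-9, 5-8 and 0-3 points.

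Sensitivity of the gain over no adjustment: R2 0, −0.7 / −0.2; R2 10%, 1.6 / 3.2; R2 60%, 13.1 / 18.6; control rate 10-15%, 5.8-8.1 / 8.2-8.8. Patient-nudge power hardly moves (about 81% in the separate simulation).

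**5. How long the list can be.** With the z-test and unit clustering, baseline SIC rate alone gives Type I error of 6.4-6.8%. Adding setting and a five-level unit-wide cancer type gives 7.7-9.0%. If those two carry no information, they cost 2.9 / 4.0 power points against the rate alone.

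**The case against.** **The general 5% threshold might define imbalance.** The plan never says that balance is judged by a hypothesis test. If it were, unit-level and patient-level 5% tests would still give 5% against 81%.

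**The precision gain is small against the rule as worded.** This stands. Read across four arms, or with a loose trigger, the rule would usually admit the covariate anyway. The larger gain needs one particular reading, a unit-level significance test.

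**The gain belongs to a covariate the plan does not list.** This also stands. For the five listed clinician- and practice-level variables (5% of variance each), fixing all five gains 0.0 / 1.9 points over a unit-level trigger and nothing over looser ones. The benefit comes from the baseline SIC rate, and the documents give no figure for its prognostic strength. The exclusion of patients with a SIC in the previous 6 months could weaken that link, and this was not simulated. At a 30% control rate power is already near its ceiling, and the gain over no adjustment is only 1.3 / 2.5 points (98.4 to 99.7%; 96.5 to 99.0%).

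**Adjustment has its own Type I cost.** True with the plan's z-test, and it rules out a long list. With errors clustered by site, as the analysis section words it, the three-variable set reaches 12.2 / 13.1%. I have no site-clustered figure for the minimal set. The mismatch between site and clinician-unit clustering is a separate point.

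**Stronger readings a reader might infer.** One is that the imbalance rule itself inflates Type I error. Step 3 shows that a single specified trigger does not; the inflation comes from choosing afterwards. Another is that such choosing has happened or is intended. Nothing in the documents says so; they only fail to exclude it.

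**Conclusion.** The concern holds as a specification weakness with a better alternative. The primary model is not determined by the plan: depending on the reading, the same unit-level covariate enters in anything from about 5% to 81% of trials. That result rests only on 66 units split evenly and 70 patients per unit. Leaving the choice open allows Type I error of about 9-10% with one covariate, against about 6%, given unit-clustered errors and the assumed control rate and R2. More candidates make it worse: free choice among subsets of three covariates (SIC rate, setting, five-level cancer type) gives 12.7-16.4%.

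The precision argument is secondary and conditional. It concerns the clinician nudge only, depends on an R2 the documents do not give, and is material only against no adjustment or a unit-level significance trigger. It would go beyond the evidence to say that fixed adjustment clearly outperforms every reading of the present rule.

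This should be changed, but it does not undermine the trial. Confidence is medium.

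**What to change.** Delete the imbalance rule. Before outcomes by arm are seen, name a minimal set that stays in the model whatever the balance:

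1. the clinician unit's SIC documentation rate before randomisation, with look-back window and denominator stated (for example, high-risk patients with a SIC-template note divided by high-risk patients seen);
2. at most, practice setting.

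Do not add a multi-level cancer type at unit level: with the z-test it takes Type I error to about 8-9%. Report the unadjusted model as a sensitivity analysis, and state that the same set applies to the secondary outcomes. Measuring the rate before clinicians are randomised matters because patients accrue afterwards and a recent SIC excludes them, so later patient-level imbalance between clinician arms need not be chance.

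**Cost.** SAP wording and one derived record-based variable. The Risks section says SIC rates are already shared with providers, and Appendix 1 shows an individual four-week count, but no pre-trial rate for a physician-APP unit is defined. The hazard ratio becomes conditional on the covariates, a small shift in simulation (mean 1.60 to 1.61 at correlation 0.1; 2.02 to 2.06 at 0.3). The plan already intends to "generate predicted probabilities of SIC documentation within 6 months, via marginal standardization", which still gives population-level results. Type I error with the z-test is about 6.3-7.0%, against 5.8-6.4% unadjusted; small-sample correction is a separate point that applies to both models.

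**Timing.** Data Collection, Aim 3 counts 1,166 completed questionnaires, and the consent-waiver section describes the Aim 3 data as already collected. That does not show that outcomes by arm have been seen. If they have, label the adjusted model post hoc.
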